4 STUDY DESIGN

4.1 Overall Design

[figure not shown]
This is a multicenter, randomized, placebo-controlled, parallel-group, double-blind Phase 2/3 operationally seamless adaptive study to evaluate the efficacy, safety, and tolerability of inhaled MK-5475 in participants with PAH. This study will be conducted in conformance with GCP principles and will be carried out in 2 parts: a Phase 2 dose selection cohort and a Phase 3 confirmatory cohort, each including a 12-week Base Period and an Extension Period.

Participants in both cohorts of this Phase 2/3 study will be adults with PAH (Groups 1.1 to 1.4), as defined in the Updated Clinical Classification of Pulmonary Hypertension (Nice, 2018) [Simonneau, G., et al 2019]. The PAH diagnosis must have been established using the updated scientific guidelines [Frost, A., et al 2019] and confirmed by a diagnostic RHC performed at any time prior to Screening. Participants will not be eligible for the study if they have been diagnosed with PH associated with left heart disease (Group 2 PH), lung disease (Group 3 PH), pulmonary artery obstructions (Group 4 PH) or PH with unclear and/or multifactorial mechanisms (Group 5 PH). All participants will continue to receive their PAH-specific background therapy during the course of the study.

For both cohorts, during the 28-day screening period (Visit 1), participant study eligibility will be assessed based on the demographic, disease diagnostic, hemodynamic, functional, echocardiographic, pulmonary function, and prior/concomitant therapy I/E criteria outlined in Sections 5.1 and 5.2. Consented participants will complete all Visit 1 procedures, as detailed in the SoAs.

Participants meeting all study entry eligibility criteria at Screening may be considered for randomization after Sponsor concurrence on key I/E criteria (See Section 8.11.2). Eligibility for study participation will be reassessed by the investigator at Randomization (Visit 2) to determine if participants continue to meet the I/E criteria and if, between Screening and Randomization, they experienced events that would exclude them for participating in the study, eg, acutely decompensated right heart failure or changes in PAH-specific therapy. Participants who have completed or prematurely discontinued the Phase 2 Cohort are not eligible to participate in the Phase 3 Cohort.

At Visit 2, participants who meet study eligibility criteria will enter the double-blind treatment period, as described below for each cohort.

Phase 2 Cohort

In the Phase 2 Cohort Base Period, 3 doses of MK-5475 ($380 \ \mu g$, $100 \ \mu g$, and $32 \ \mu g$) will be compared to placebo. The efficacy, safety, and tolerability of each MK-5475 dose will be assessed when all participants in the Phase 2 Cohort Base Period have completed or discontinued the 12-week treatment period. An IA for efficacy and futility (nonbinding) is

planned when approximately 120 participants have completed or discontinued the Phase 2 Cohort Base Period. The Phase 2 Cohort Base Period may stop at the IA and a dose for the Phase 3 Cohort may be selected at that time OR the study may be stopped early for futility (Section 9.7).

The primary objective of the Phase 2 Cohort Base Period is to evaluate the effect of MK-5475 versus placebo on PVR in participants with PAH at Week 12. Of the 3 MK-5475 doses studied, the dose (380 μ g, 100 μ g, or 32 μ g) with the best efficacy and safety profile in the Base Period of this cohort will be selected for evaluation in the subsequent Phase 3 confirmatory cohort, alongside a placebo control group.

Participants who remain on study intervention and complete the Visit 6/Week 12 assessments (*including RHC*) may enroll in the ~40-month blinded Extension Period if they satisfy the SpO₂ and seated BP study eligibility criteria (Section 5.2) at Week 12 and provide documented informed consent. Participants who discontinue study intervention or complete the Phase 2 Cohort Base Period before Amendment 01 is approved and the Extension Period becomes available will not be eligible to enroll in the Extension Period.

The objective of the Phase 2 Cohort Extension Period is to evaluate the longer-term safety and tolerability of the 3 doses of MK-5475 (380 μ g, 100 μ g, or 32 μ g) in this participant population.

To supplement the routine blinded trial monitoring outlined in this study, an external DMC will monitor the interim data (Section 9.7).

This Phase 2/3 study may be stopped if analysis of the data collected either at the time of the IA or at the end of the Phase 2 Cohort Base Period shows that none of the MK-5475 doses has a desirable efficacy and safety profile.

Participants will take part in the Phase 2 Cohort Base Period for approximately 16 weeks, including a screening period of up to 4 weeks and a 12-week double-blind treatment period. Approximately 164 eligible participants will be randomized in a 1:1:1:1 ratio to MK-5475 380 μ g, MK-5475 100 μ g, MK-5475 32 μ g, and placebo. Participants will be instructed to inhale 1 dose per day, in the morning, for 84 consecutive days. At the end of the 12-week treatment period, pulmonary vascular hemodynamics will be assessed via RHC, following the same procedures as for the baseline measurements. In the Extension Period, the participants who received placebo during the Base Period will initially be assigned randomly in a 1:1:1 ratio to once-daily dosing with 1 of the 3 doses of MK-5475 (380 μ g, 100 μ g, or 32 μ g) and will be given new randomization numbers. The participants who received MK-5475 during the Base Period will initially receive the same MK-5475 doses in the Extension Period and will be assigned new randomization numbers, to maintain study blinding.

After selection of the MK-5475 dose for Phase 3, the 3 MK-5475 dose groups in the Phase 2 Cohort Extension Period will be collapsed into a single dose group for the remainder of the Phase 2 Cohort Extension Period.

Phase 3 Cohort

In both the Base and the Extension Period of the Phase 3 Cohort, the MK-5475 dose (either $380 \ \mu g$, $100 \ \mu g$, or $32 \ \mu g$) selected in the Phase 2 Cohort Base Period will be compared to placebo. The primary objective for the Base Period of Phase 3 Cohort is to evaluate the effect of MK-5475 versus placebo on 6MWD in participants with PAH at Week 12. The Base Period will be followed by a double-blind Extension Period, to further inform on the efficacy, safety, and tolerability of MK-5475 in this participant population.

In the Phase 3 Cohort Base Period, participants will take part in the study for approximately 16 weeks, including a screening period of up to 4 weeks and a 12-week double-blind treatment period. Approximately 286 eligible participants will be randomized in a 1:1 ratio to MK-5475 and placebo. Participants will be instructed to inhale 1 dose per day, in the morning, for 84 consecutive days. 6MWD will be measured, using the same procedure as for the baseline measurement, every 4 weeks and at the end of Phase 3 Cohort Base Period. All participants will continue treatment in an Extension Period until a requisite number of clinical worsening events are observed in the Phase 3 Cohort and a second Phase 3 study. The second Phase 3 study will be described in a separate protocol. A separate integrated analysis plan will be written, providing more details. A CAC, whose members are blinded to the study group assignments, will review all reported clinical events and adjudicate the clinical events related to clinical worsening (See Appendix 1).

In both Phase 2 and Phase 3 Cohorts, additional hemodynamic parameters, changes in symptoms, biomarkers, and participant self-rated quality-of-life questionnaire scores will be used to evaluate response to treatment throughout the study.

Selected members of the Sponsor study team and management will be unblinded to results from Phase 2 Cohort Base Period and Phase 3 Cohort Base Period, to evaluate the efficacy and safety profile of MK-5475 (Section 9.7). For the Phase 2 Cohort Extension Period and Phase 3 Cohort Extension Period, separate blinded Sponsor study teams will monitor the ongoing study.

For each cohort, the double-blind treatment period concludes with a final visit. All participants will complete a telephone follow-up visit 14 days (+ 2 days) after the final visit, for AE monitoring.

AEs will be monitored throughout the study and graded in severity according to the guidelines outlined in Section 10.3.4. Regular safety assessments will be performed during the study (Section 8.3.9).

To supplement the routine trial monitoring outlined in this study, an external DMC will monitor interim data (Section 9.7).

Specific procedures to be performed during the study, including prescribed times and associated visit windows, are outlined in Section 1.3 of the SoA. Details of each procedure are provided in Section 8.

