1.2 Schema

The study design for Phase 2 Cohort is depicted in Figure 1. The study design for Phase 3 Cohort is depicted in Figure 2.

[figure not shown]

Figure 1 Study Design – Phase 2 Cohort

6MWT=6-minute walk test; CRF=Case Report Form; FV=Final Visit; PAH=pulmonary arterial hypertension; PFT=pulmonary function tests; QD=once daily; R=randomization; RHC=right heart catheterization; TC=telephone contact; V=visit; V_{Wk24}=Visit at Week 24; Wk=Week.

^a The diagnosis of PAH should be confirmed by RHC.

^b An interim analysis for efficacy and futility (nonbinding) is planned when CCI have completed or discontinued Phase 2 Cohort Base Period.

^c The participants who received MK-5475 during the Base Period will initially receive the same MK-5475 doses in the Extension Period. The participants who received matching placebo during the Base Period will initially be randomized 1:1:1 to receive 1 of 3 MK-5475 doses (380 µg, 100 µg, or 32 µg). After selection of the MK-5475 dose for Phase 3, the 3 MK-5475 dose groups in the Phase 2 Cohort Extension Period will be collapsed into a single dose group for the remainder of the Phase 2 Cohort Extension Period (Section 4.1). Participants will be reassigned to the selected single dose group at their next scheduled visit. ^d Screening procedures will be performed over multiple days and should be performed in order (See Study Operations Manual). Data collected during the 28-day screening period will be registered as Visit 1 in the CRE.

^c The participants who complete the Base Period and provide documented informed consent for the Extension Period may be enrolled. The participants who complete the Base Period before Amendment 01 approval by the study site are not eligible.

^f Visit 3 and TC are telephone visits.

⁸ Visit 6 procedures may be performed over multiple days.

^h Visit 6 is the last visit for the Base Period and the Baseline Visit for the Extension Period.

For participants who complete the Base Period and enroll in the Extension Period, TC occurs the day after Visit 6 (+2 days). For participants who complete the Base Period but do not continue in the Extension Period, TC occurs 14 days after V6 (+2 Days).

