9.6.1.1 Phase 2 Cohort

In the Phase 2 Cohort, efficacy endpoints will be collected during the Base and Extension Periods. For the Base Period, the analysis timepoint of interest is Week 12. For the Extension Period, the analysis timepoint of interest is Week 24. Summary statistics will be provided for every planned data collection timepoint described in the SoA (Section 1.3).

Primary Endpoint

Following the ICH E9 (R1) guidance [European Medicines Agency 2020], The primary estimand for the primary objective used for the Phase 2 Cohort contains 5 attributes:

• The treatment condition of interest is MK-5475 or matching placebo with stable concomitant PAH-specific therapy, as defined in Section 5.1.

- The population of participants targeted by the clinical question are male/female participants with PAH between the ages of 18 and 75 years (inclusive).
- The variable to address the clinical question is PVR at Week 12.
- The following are intercurrent events, along with the approaches to handle them:
 - Death: hypothetical strategy to evaluate PVR at Week 12 as though death would not occur.
 - Treatment discontinuation: treatment policy strategy seeking to use every participant's actual Week 12 value, regardless of whether they are still taking study medication.

The approach to handling missing data for these intercurrent events is described below.

• The population-level summary is mean percent change from baseline in PVR at Week 12.

For this estimand, the primary approach will use a robust regression method to address the primary hypothesis. Robust regression method will be used because percent change from baseline in PVR is not expected to follow a normal distribution, based on other Phase 2 clinical trials which have used non-parametric methods for analyzing PVR [Simonneau, G., et al 2012] [Ghofrani, H. A., et al 2010]. The robust regression model will include terms for treatment and WHO-FC (Class II and Class III/IV). Missing PVR observations at Week 12 from participants in all treatment groups will be imputed following a PMM. Missing data due to death will be imputed as the worst outcome among all observed data. Missing data due to treatment discontinuation will be imputed based on the observed PVR observations at Week 12 from the placebo group referred as J2R (detailed below). If there are missing Week 12 data for other reasons, J2R will also be used. The randomization seed for imputations will be 5475007.

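### The Phase 2 Extension objective names three doses, but two of them end at Phase 3 dose selection and the safety rules do not split the data at that switch

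*Combined protocol and SAP*

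**What the plan says.** - **Objective (4.1).** "The objective of the Phase 2 Cohort Extension Period is to evaluate the longer-term safety and tolerability of the 3 doses of MK-5475". Participants who complete Week 12 "may enroll in the ~40-month blinded Extension Period".
- **Starting dose (4.1).** "The participants who received MK-5475 during the Base Period will initially receive the same MK-5475 doses in the Extension Period". For the others, "the participants who received placebo during the Base Period will initially be assigned randomly in a 1:1:1 ratio to once-daily dosing" with one of the three doses.
- **Collapse (4.1, repeated in 1.1, 2.1, 6.3.1 and 6.6).** After the Phase 3 dose is chosen, "the 3 MK-5475 dose groups in the Phase 2 Cohort Extension Period will be collapsed into a single dose group for the remainder" of that period. Section 9.1 applies this to everyone in the Extension, whatever their randomized group. A Figure 1 footnote in 1.2 gives the timing: "Participants will be reassigned to the selected single dose group at their next scheduled visit".
- **When selection can happen (4.1).** At the interim analysis, when about 120 participants have completed or discontinued the Base Period, or after the full Base Period of about 164.
- **Regimen tables (1.1, and Table 2 in 6.1).** Groups 1 to 3 are each listed at one fixed dose for the Base Period and the whole Extension. A row for the time after dose selection exists only for Groups 4a to 4c.
- **Safety population (9.5.2).** The same population serves both periods. Participants count in their randomized group unless they took incorrect treatment throughout the treatment period.
- **Safety analysis (9.6.2).** The end-of-Extension analysis uses Base and Extension data together.
- **Efficacy (9.6.1.1).** "For the Extension Period, the analysis timepoint of interest is Week 24".

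**The concern.** The objective reads as a by-dose statement for all three doses, but the design can sustain longer-term observation of only one of them. Once a dose is chosen, nobody is planned to stay on either of the other two. How long a participant stays on an unselected dose depends on when that person enrolled and when the decision is made, and the plan fixes neither.

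The analysis rules make this more than a wording problem. A participant moved by design to the selected dose has not taken incorrect treatment, so the exception in 9.5.2 does not apply and the person stays in the randomized group. With the two periods pooled under 9.6.2, an event on the selected dose after the switch is tabulated under a dose the participant no longer takes. That would blur dose differences in the final Phase 2 report, including for symptomatic hypotension, a prespecified safety topic in 9.6.2.1.

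**Working it through.** The plan gives no figure for Extension exposure by dose, so there is none to reproduce. The check has three parts.

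**1. How many participants could be affected.** From 4.1, 164 are randomized 1:1:1:1, so 164/4 = 41 per group. If everyone continued, each dose would start the Extension with 41 + 41/3 ≈ 55 participants. The two unselected doses together would have about 109. These are ceilings, because dropout and the Amendment 01 eligibility rule reduce them.

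**2. How long participants stay on the initial dose.** The documents state neither the enrollment period nor the time to selection. Assumptions:

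- uniform enrollment over R = 6 to 24 months;
- selection L = 1 to 6 months after the last Week 12 visit (full Base Period);
- a mean wait of half a 6-week visit interval, 3 weeks or 0.69 months, until the next visit;
- either none, or the earliest 25%, of enrollees barred by the Amendment 01 rule.

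Formulas for Extension time on the initial dose:

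- Mean, none barred: R/2 + L + 0.69. Mean, earliest 25% barred: 0.375R + L + 0.69.
- Last enrollee: L + 0.69. First eligible enrollee: R + L + 0.69, or 0.75R + L + 0.69 with 25% barred.

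The last column adds the 12 Base weeks (2.76 months) and applies to participants on active drug from the start. Paired entries are none barred / 25% barred.

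| R, L (months) | Mean | Last | First | At least 12 months in total on initial dose |
|---|---|---|---|---|
| 6, 1 | 4.7 / 3.9 | 1.7 | 7.7 / 6.2 | 0% / 0% |
| 12, 3 | 9.7 / 8.2 | 3.7 | 15.7 / 12.7 | 54% / 38% |
| 24, 6 | 18.7 / 15.7 | 6.7 | 30.7 / 24.7 | 89% / 86% |

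The mean is thus about 4 to 19 months, and individual times run from about 1.7 to 31 months. The share with at least 6 months in total on the initial dose is 66% to 100%. Selection at the interim would shorten all of these times.

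**3. How much time could be misattributed.** For a participant who stays the full ~40 months, average time after the switch is 40 − 18.7 = 21.3 to 40 − 3.9 = 36.1 months. That is 53% to 90% of the Extension. For a participant who started on an unselected dose, 9.5.2 and 9.6.2 place all of it under that unselected dose.

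**Week 24.** Weeks are numbered from randomization, so Week 24 falls 12 weeks into the Extension. A participant's Week 24 value follows a dose change only if reassignment comes within about 12 weeks of entry. With L = 3 months (about 91 days), even the last enrollee passes 84 days plus the 5-day window (89 days) before the switch. With L = 1, or with selection at the interim, some late enrollees would not.

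**The case against.** Much of the opposing case is sound.

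- A reader might infer that two doses get no long-term exposure. The documents do not support that. All three doses accrue Extension time until selection and the next visit, and the visit-frequency rule in 1.2 provides for participants already at Weeks 24, 36, 48 and 60.
- A reader might take ~40 months as the length of observation promised for each dose. The objective sets no duration; the ~40 months describes the Extension. The safety objective in Section 3 concerns MK-5475 as a whole.
- A reader might treat the 164 − 120 = 44 participants (27%) not yet through the Base Period at the interim as having almost no further time on their own dose. That is at most an upper bound. It needs a near-zero decision lag and full enrollment although the Base Period may stop there, and it counts people already on the selected dose.
- A reader might say that by-dose safety is confounded with calendar time. Before the switch the doses ran concurrently under randomization, so follow-up should be balanced across them. The difficulty lies in pooling data from after the switch.
- Section 9.6.1 makes no statistical comparisons for the Extension, and the Table 7 footnote removes between-group intervals and graphs. Section 9.12 already plans an exposure summary, with details left to the supplemental SAP. Extension 6MWD at Week 24 is exploratory, with methods deferred to that document, and 9.6.1.1 does not say that the Week 24 summary is by dose.

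These points limit the finding but do not remove it. Descriptive by-group tables remain, and misattribution affects counts and percentages as much as intervals. The objective and the population rule both stand in this document, and neither provides for the switch.

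**Conclusion.** The point holds in a limited form. The stated objective does not fit a design that moves everyone to one dose. Exposure to the two unselected doses is truncated at selection, of unspecified length and unequal between participants. Followed as written, the safety rules would report events on the selected dose under unselected doses.

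The mean of about 4 to 19 months on the initial dose rests on assumed enrollment and decision times, with selection after the full Base Period. The mismatch and the attribution gap do not depend on those assumptions, only on a dose being selected; if none is, no collapse is triggered. The Week 24 issue is secondary and arises only when reassignment comes within about 12 weeks of Extension entry. The effect is on what the final Phase 2 report can say about each dose. The Phase 2 primary analysis is not affected.

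**What to change.** 1. **Section 4.1.** Restate the objective as longer-term safety and tolerability of the dose selected for Phase 3, with safety of the three doses described up to reassignment.
2. **Sections 9.5.2 and 9.6.2.** For participants whose dose changes, end the by-dose safety summaries at reassignment and report later events and exposure under the selected dose. Participants already on that dose need no cut.
3. **Section 9.12 or the supplemental SAP.** Show the exposure achieved on each dose, for example the number with at least 6 and at least 12 months, beside any by-dose statement.
4. **Section 9.6.1.1.** If a Week 24 Extension summary is given by dose, exclude only participants whose dose actually changed before that visit. Excluding everyone seen after the reassignment date would discard single-dose data from those already on the selected dose.
5. **Section 1.1 and Table 2.** Reconcile the rows for Groups 1 to 3 with the collapse rule. Which regimen is intended is for the sponsor to state.

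The cost is wording in the objective and the SAP, plus one exposure table. The downside is a narrower claim for the two unselected doses. No change to dosing is proposed.

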4.2 Scientific Rationale for Study Design

This operationally seamless adaptive Phase 2/3 study is being conducted to evaluate the efficacy, safety, and tolerability of MK-5475 for the treatment of PAH, when added to PAH-specific background therapy. The conduct of this study is supported by evidence from preclinical and clinical studies, in which MK-5475 appeared to be safe and well tolerated, and in which proof of concept has been established - single doses of MK-5475 can effectively reduce PVR, without inducing systemic hypotension in this patient population.

The operationally seamless adaptive design, by combining into a single study objectives which otherwise would have been evaluated in 2 separate studies, will reduce the development timelines while using the same operational infrastructure. The study team will select a dose for the Phase 3 Cohort after reviewing all safety and efficacy information collected in the Phase 2 Cohort Base Period. Given the severity of the disease and the unmet medical need, this study design allows expedited clinical drug development and accelerated timeline for potential registration and patient access, while ensuring study integrity [Food and Drug Administration 2019].

